COMIRB Protocol

COLORADO MULTIPLE INSTITUTIONAL REVIEW BOARD
[name] [contact] [contact]

Project Title: Evaluation of speech-in-noise performance in cochlear implant recipients using either a conventional hearing aid or a CROS device on the contralateral ear

Version: January 30, 2019

Principal Investigator: [name]

COMIRB #: 18-1101

I. Hypotheses and Specific Aims:

Speech understanding in noise remains the greatest challenge for individuals utilizing cochlear implants, particularly when the speech of interest originates from the side of the head opposite to the implant. Recent advances in hearing technology allow for an individual to either use a conventional hearing aid or a Contralateral Routing of Signal (CROS) device on the non-implanted ear. Differences in speech understanding may result depending on the specific device chosen by an individual, and these differences may be measureable through speech discrimination measurement protocols.

Hypotheses:

1. Performance on a speech perception task will vary based on the type of amplification device a listener uses on the ear contralateral to the cochlear implant
2. As the originating locations of the speech and noise are varied, the amount of benefit seen by specific device configurations (cochlear implant + hearing aid or cochlear implant + CROS) will also vary.
3. Perceived listening effort will vary as device and speech/noise original locations are varied

Specific Aims:

1. Quantify the changes in speech in noise perception for adults using a cochlear implant in one ear as the device on the contralateral ear is varied.
2. Quantify the changes in speech in noise perception for adults using a cochlear implant in one ear as the originating locations of the speech and noise are varied.
3. Quantify the self-reported amount of listening effort perceived by a listener when listening to speech in noise for a variety of device and speech/noise location configurations.

Consented subjects will fill out a case history form and participate in various speech and hearing tests under 7 conditions which will provide data on which device condition produced the best speech perception in noise results.

This study intends to determine whether or not a CROS device improves speech perception in noise when the source of the speech of interest originates from the side of the head opposite to the implant.

II. Background and Significance:

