Speech perception in noise continues to be the greatest challenge for unilateral cochlear implant users, most notably when the desired speech signal is presented to the ear opposite of their cochlear implant processor. Recent advances in hearing technology, as well as the expansion of candidacy criteria for cochlear implantation, has allowed for more individuals with one cochlear implant to take advantage of a device in their non-implanted ear. For those individuals with aidable hearing (thresholds better than 70 dB at any frequency) in the non-implanted ear, the benefit of bimodal hearing (cochlear implant + hearing aid in the non-implanted ear) has been well documented: access to low-frequency acoustic information provides fine-structure and spectral resolution that is lost with the envelope-based signal process strategies of a cochlear implant (Ching, et al., 2004, 2007 ; Gifford, et al., 2007; Zhang, et al., 2010; Dunn, et al., 2005; Morera, et al., 2004). However, for many individuals, the bimodal condition does not provide additional benefit over the cochlear implant alone (Dorman, et al., 2014; Gifford, et al., 2015; Veugen, et al., 2016; Vroegop, et al., 2018). For example, factors that may limit benefit are the level of CI only performance, the degree of hearing loss in the non-implanted ear, and the variety of complex listening conditions (Dorman, et al., 2015; Ching et al., 2007). For those individuals with either objective or subjective lack of benefit from a contralateral hearing aid despite aidable thresholds, a contralateral routing of signal (CROS) device could provide benefit when listening to speech in noise (Ryu, et al., 2014; Kitterick, et al., 2014). In patients with unilateral hearing loss, CROS technology has shown to have both subjective and objective benefits for speech perception in noise and sound localization, however, there is limited or no benefit when noise is presented to the affected ear (noise on the side of the CROS device) (Ryu, et al., 2014). For unilateral cochlear implant users, the difference in benefit of speech perception in noise when using a conventional hearing aid versus a CROS device may be measurable through speech discrimination measurement protocols. For unilateral cochlear implant users, the difference in benefit of speech perception in noise when using a conventional hearing aid or a CROS device may be measurable through speech discrimination measurement protocols.

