Cochlear Implant Information	Collect information regarding cochlear implant (date of surgery, specifications of internal and external cochlear implant equipment)
Datalogging	Characterize typical listening environment of participant as identified by the cochlear implant datalogging

Test Type	Purpose	Standard Test	Description	Length of Time
Informed Consent	Assure participant is providing consent prior to			15 minutes

Test Type	Purpose	Standard Test	Description	Length of Time
	initiating any study tasks			
Case History	Capture information regarding the subject's hearing and cochlear implant/ hearing aid history	Case History Questionnaire (attached)	Questionnaire queries history of cochlear implant and hearing aid use, medical history related to hearing health and auditory system, and other factors that may influence hearing status.	10 minutes
Hearing Evaluation	Quantify the hearing status of the subject	pure tone air and bone conduction	Assess unaided thresholds for both right and left ears, assess cochlear-implant aided thresholds.	20 minutes
Hearing Device Fitting	Program the hearing aid and CROS device	Fitting/Real ear measures of hearing aid and link CROS with CI	Assess amount of sound in ear canal to assure that sound is appropriately audible based on hearing loss of non-implanted ear.	30 minutes
Speech Perception in Noise Test	Quantifiable measurement of a subject's ability to process speech in an environment with competing sound	Sentence in noise assessment	Sentences are presented with competing noise. Speech will be presented at 60 dBA. Level of noise will be adaptive, and will assess the SNR needed for 50% correct. Specific conditions are noted below.	10 minutes per condition (150 minutes total)
Listening effort and acceptability rating scales	Obtain subjective rating of the degree of difficulty and desirability presented by each listening condition	Listening Effort and Acceptability Scale (attached)	Following each speech-in-noise condition, the listener will rate the amount of effort required to complete the task and the acceptability for listening with the assessed device settings.	Included in speech-in-noise conditions above

Conditions assessed for Speech Perception:

1. Speech presented at non-CI side (CI only) and noise presented diffusely
2. Speech presented at non-CI (CI+HA ON) and noise presented diffusely
3. Speech presented at non-CI (CI+CROS ON) and noise presented diffusely

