4. Speech presented at CI side and noise presented diffusely (CI only)
5. Speech presented at CI side and noise presented diffusely (CI+HA ON)
6. Speech presented at CI side and noise presented diffusely (CI+CROS ON)

7. Speech presented to the front, noise presented diffusely (CI-only)
8. Speech presented to the front, noise presented diffusely (CI+HA ON)
9. Speech presented to the front, noise presented diffusely (CI+CROS ON)

10. Speech presented at non-CI side (no device) and noise presented at CI-ear (+90° and -90°)
11. Speech presented at non-CI side (CI+HA ON) and noise presented at CI-ear (+90° and -90°)
12. Speech presented at non-CI side (CI+CROS ON) and noise presented at CI-ear (+90° and -90°)

13. Speech and noise presented from front (CI only)
14. Speech and noise presented from front (CI+HA ON)
15. Speech and noise presented from front (CI+CROS ON)

Description of procedures and related risks:

Test	Risk	Rationale
All	Accidental sharing of information	Because patients are recruited into this study, this study could not be done without the use of some PHI for contacting subjects.
Speech Perception in Noise Test	Boredom	Speech Perception testing poses very little risk to subjects. Each of the evaluations proposed here are standard clinical protocols.

Minimizing risks:

In order to minimize the risk of unintentionally sharing research data, paper records (which is limited to the informed consent/HIPAA B combined document) will be stored in a locked cabinet secured to a wall. In addition, access to electronic records will be limited to only study personnel. Subjects will be offered breaks if they feel tired, bored or an inability to concentrate.

Other risks:

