Study data will be collected and managed using REDCap (Research Electronic Data Capture). REDCap is a secure web application designed to support data capture for research studies, providing user-friendly web-based case report forms, real-time data entry validation (e.g. for data types and range checks), audit trails and a de-identified data export mechanism to common statistical packages (SPSS, SAS, Stata, R/S-Plus). The system was developed by a multi-institutional consortium which includes University of Colorado–Denver and was initiated at Vanderbilt University. The database is hosted at the University of Colorado–Denver Development and Informatics Service Center (DISC), which will be used as a central location for data processing and management. REDCap data collection projects rely on a thorough study-specific data dictionary defined in an iterative self-documenting process by all members of the research team with planning assistance from the DISC. This iterative development and testing process results in a well-planned data collection strategy for individual studies. REDCap also includes a powerful tool for building and managing online surveys. The research team can create and design surveys in a web browser and engage potential respondents using a variety of notification methods. REDCap is flexible enough to be used for a variety of types of research and provides an intuitive user interface for database and survey design and data entry.

E. Potential Scientific Problems:

There are no known scientific problems at this time.

F. Statistical Analysis Plan

Sample Size Estimate:

The standard deviation for speech reception thresholds (SRTs) for individuals with cochlear implants was used for an estimate of within group variation. This value, obtained from a similar analysis of an Advanced Bionics device versus a Cochlear Corporation device (Gifford & Revit 2010), is estimated to be 3.2 dB.

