This study will utilize a modified eight-period crossover design for the two treatments, where 4 sequences will be used for each hearing device. A power analysis was conducted using simulations to detect a difference in speech reception thresholds of 2 dB between two groups at an alpha level of 0.05. A sample size of 14 subjects total provides 90% power to detect a difference in speech reception thresholds of 2 dB. To assess the accuracy of these simulations, other non-simulated power analyses showed similar results, even though these methods do not directly apply this study's design. This change of 2 dB is a clinically meaningful difference that we consider a realistic expectation of the intervention, the CROS device, in this study. Although no attrition is expected, we will recruit up to 50 subjects which will give more power so that the interactions can be estimated more accurately.

Statistical Analysis Plan:

Statistical analysis will be carried out using SAS. A linear mixed model will be fit with SAS PROC MIXED using a random subject effect. The primary outcome, speech reception threshold (dB), will be regressed on the main effect of treatment (CROS hearing device vs. conventional hearing aid), signal location (directly to the CI ear vs. opposite), and noise location (directly to the subject's non-CI ear vs. diffuse in the room), as well as the interactions between device type and locations. This method provides valid handling of occasional missing observations. Contrasts will be used within the model to estimate both overall effects and differences in conditions.

G. Summarize Knowledge to be Gained:

This study intends to determine whether or not a conventional hearing aid or a CROS device utilized on the ear contralateral to cochlear implantation improve speech perception in noise when the source of the speech of interest originates from the side of the head opposite to the cochlear implant.

H. References:

Bronkhorst, A. W., & Plomp, R. (1988). The effect of head-induced interaural time and level differences on speech intelligibility in noise. *The Journal of the Acoustical Society of America*, 83(4), 1508-1516.

Cherry, E. C. (1953). Some experiments on the recognition of speech, with one and with two ears. *The Journal of the acoustical society of America*, 25(5), 975-979.

Ching, T. Y., Incerti, P., & Hill, M. (2004). Binaural benefits for adults who use hearing aids and cochlear implants in opposite ears. *Ear and hearing*, 25(1), 9-21.

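### The primary model has no CI-only level, so it can compare CROS with a hearing aid but cannot show whether either device improves speech perception when speech comes from the side opposite the implant.

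*Combined protocol and SAP*

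**What the plan says.** **The question.** Section I closes with "This study intends to determine whether or not a CROS device improves speech perception in noise" when speech comes from the side opposite the implant. Section G asks the same of both a conventional hearing aid and a CROS device. Hypothesis 1 is more general: "Performance on a speech perception task will vary based on the type of amplification device a listener uses" on the contralateral ear. Section II judges bimodal benefit against the implant alone: "for many individuals, the bimodal condition does not provide additional benefit over the cochlear implant alone".

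**The data.** Section IV.D lists 15 conditions, five speech/noise configurations by three device states. The reference state appears, for example, as "Speech presented at non-CI side (CI only) and noise presented diffusely" (condition 1) and "Speech presented to the front, noise presented diffusely (CI-only" (condition 7). Condition 10 is labelled differently: "Speech presented at non-CI side (no device) and noise presented at CI-ear".

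**The analysis.** Section IV.F describes one linear mixed model with a random subject effect. The SRT "will be regressed on the main effect of treatment (CROS hearing device vs. conventional hearing aid". The other terms are signal location (CI ear or opposite), noise location (non-CI ear or diffuse) and the device-by-location interactions. Overall effects and condition differences are to come from contrasts within that model. The documents describe no other analysis of the CI-only data.

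**The sample size.** It is built on two treatments in eight periods. The SRT standard deviation "is estimated to be 3.2 dB", and 14 subjects are said to give 90% power for 2 dB at alpha 0.05. Enrolment may reach 50.

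**The concern.** Improvement is a difference from listening without a contralateral device, and the planned treatment effect contains no such term. In (CROS − CI only) − (HA − CI only) the CI-only mean cancels, leaving CROS − HA. Three situations show what is lost:

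- CROS helps by 2 dB and the hearing aid does nothing: the CROS advantage is 2 dB.
- CROS does nothing and the hearing aid worsens the SRT by 2 dB: the CROS advantage is again 2 dB.
- Both devices help by 2 dB: the difference is 0.

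The trial could follow its plan exactly and finish without a prespecified answer to section G. Any statement about improvement would then rest on contrasts chosen after the data are seen, with no power statement behind them.

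**Working it through.** **1. Which conditions fit the model.** Each condition in section IV.D is set against the factor levels in section IV.F.

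| Conditions | Speech | Noise | CI only | CI+HA | CI+CROS |
|---|---|---|---|---|---|
| 1–3 | non-CI side | diffuse | 1: no device level | 2: fits | 3: fits |
| 4–6 | CI side | diffuse | 4: no device level | 5: fits | 6: fits |
| 7–9 | front | diffuse | 7: no device level | 8: no location level | 9: no location level |
| 10–12 | non-CI side | CI ear | 10: no device level | 11: no location level | 12: no location level |
| 13–15 | front | front | 13: no device level | 14: no location level | 15: no location level |

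Four conditions fit. Eleven do not: 5 on device and a further 6 on location. At 10 minutes per condition that is 11 × 10 = 110 of 150 test minutes; at 50 subjects it is up to 11 × 50 = 550 of 750 SRTs. The CI-only gap alone accounts for 5 conditions, 50 minutes and up to 250 SRTs. No listed condition supplies the model's noise level at the non-CI ear.

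**2. Estimability.** A rank check on a device-by-location design matrix shows that with two device levels CROS − HA is estimable but CROS − CI only and HA − CI only are not. With three levels all three are. Adding only the device level to the planned model brings in conditions 1 and 4, so CROS − CI only is available in two configurations (3 vs 1, 6 vs 4). Matching the location levels as well makes it available in all five, once condition 10 is reconciled.

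**3. Reproducing the stated sample size.** Inputs: difference 2 dB, SD 3.2 dB, alpha 0.05 (two-sided assumed), power 90%.

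- Observations per device = 2 × (3.2 × (1.960 + 1.282) / 2)² = 53.8.
- With four observations per device per subject: 53.8 / 4 = 13.45, so 14 subjects.

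This matches the plan when 3.2 dB is the residual SD, there are exactly two devices, and each is observed four times per subject.

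**4. Power for a device-minus-CI-only contrast.** For k configurations averaged, SE = 3.2 × √(2/(n·k)). Power is from the noncentral t with 14(n − 1) degrees of freedom (15 conditions per subject, random subject effect), 2 dB, two-sided 0.05.

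| k | SE at n=14 | Power, n=14 | Power, n=50 | n for 90% |
|---|---|---|---|---|
| 1 (3 vs 1) | 1.209 | 37.7% | 87.7% | 54 |
| 2 (also 12 vs 10) | 0.855 | 64.3% | 99.3% | 28 |
| 4 (the reading in step 3) | 0.605 | 90.8% | over 99% | 14 |

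The normal approximation gives 27 rather than 28 for k = 2 (53.8 / 2 = 26.9).

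**5. If 3.2 dB is a total SD.** Residual SD = 3.2 × √(1 − ρ), with ρ the within-subject correlation. The documents do not give ρ; 0.3 to 0.7 is assumed. For k = 1:

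| ρ | Residual SD | Power, n=14 | Power, n=50 | n for 90% |
|---|---|---|---|---|
| 0.3 | 2.68 | 50.2% | 96.2% | 38 |
| 0.5 | 2.26 | 64.3% | 99.3% | 28 |
| 0.7 | 1.75 | 85.2% | over 99% | 17 |

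**6. If alpha is split over the two device-versus-CI-only contrasts** (0.025 each, residual SD 3.2 dB, normal approximation): for k = 1, power is 28% at 14 and 81% at 50, with 64 subjects for 90%; for k = 2, 54% and 98.5%, with 32 subjects.

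**The case against.** **Head-to-head is a legitimate main question.** The project title, Aim 1 and much of section II frame it that way, and the model answers it. The closing sentence of section I names no comparator and could mean CROS relative to a hearing aid. That stands. Section G is the firmer basis: it names both devices, so improvement must be relative to neither.

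**The contrast sentence may be meant to cover CI-only.** Section IV.F promises condition differences, and the listed conditions include CI-only, so the treatment parenthesis may name only the main comparison. But the contrasts are to be made within the model, and the sample-size text also counts two treatments. The condition list does limit the relevant contrasts to 2 or 3 vs 1 and 11 or 12 vs 10, so the scope for post-hoc choice is small, though not nil.

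**Eleven of 15 mixes two defects.** This is fair: the missing CI-only level explains five, and the location mismatch would exist without it. If noise at the non-CI ear in section IV.F and noise at the CI ear in section IV.D are the same setup with one mislabelled, conditions 11 and 12 fit and the count falls to nine. The cause may be text that was never aligned: section I mentions 7 conditions, sections IV.C and IV.D mention 15, and the sample size uses eight periods.

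**Power may be adequate in practice.** At 50 subjects it is 88% or higher under either SD reading for an unsplit alpha. But 50 is a ceiling, and the only number the plan justifies is 14. Four observations per device is also an inference, because the sponsor's simulation is not shown; it rests on the arithmetic match.

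**Conclusion.** The concern holds. Followed as written, the plan leaves the question in section G without an analysis, although the data to answer it are collected. No device-minus-CI-only contrast is estimable. On a literal reading 11 of 15 conditions fall outside the model, five of them because the device level is missing.

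The 90% power at 14 subjects does not transfer to a single-configuration benefit contrast: about 38% if 3.2 dB is the residual SD, and about 50% to 85% if it is a total SD with correlation 0.3 to 0.7. These figures assume a 2 dB effect, two-sided 0.05, no multiplicity adjustment and no missing data. The estimability finding depends on none of them. This should be fixed before the data are analysed; no data are lost, so it is not a flaw in the conduct of the trial.

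**What to change.** 1. Make device a three-level factor: CI only, CI+HA, CI+CROS.
2. Replace the two location factors with one five-level speech/noise configuration factor matching section IV.D, or extend their levels to cover front speech, front noise and noise at the CI ear. Keep the device-by-location interaction. Extending the factors preserves the separate location effects that Aim 2 concerns.
3. Prespecify CI+CROS and CI+HA each minus CI only with speech at the non-CI side: 3 vs 1 and 2 vs 1, plus 12 vs 10 and 11 vs 10 once the label of condition 10 is reconciled with that of 1, 4, 7 and 13.
4. Keep CROS versus hearing aid as the comparison the sample size was built for.
5. State which contrast is primary, how multiplicity is handled, and whether 3.2 dB is a residual or a total SD. Report power for the CI-only contrasts separately from the 14-subject figure.

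The cost is SAP text and a few power statements; no visits or tests are added. If a single-configuration CI-only contrast becomes primary, the sample size must be redone: about 54 subjects for 90% power with 3.2 dB as residual SD, above the cap of 50, or 17 to 38 under the total-SD reading. Averaging the two non-CI-side configurations needs about 28 in the residual-SD case.

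### The SAP's location factors do not match the listed test conditions: read literally, 6 of the 10 hearing-aid/CROS conditions have no place in the model and device-by-noise cannot be estimated

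*Combined protocol and SAP*

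**What the plan says.** Section IV.F (Statistical Analysis Plan) regresses the speech reception threshold on device (CROS or hearing aid) and on two location factors. For speech, the factor reads "signal location (directly to the CI ear vs. opposite"). For noise, it reads "noise location (directly to the subject's non-CI ear vs. diffuse in the room"). Each location factor may also interact with device; the plan's words are "as well as the interactions between device type and locations". On how results will be drawn from the model, it states: "Contrasts will be used within the model to estimate both overall effects and differences in conditions". No weights are given for the overall effects.

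The sample size text in the same section describes a "modified eight-period crossover design for the two treatments, where 4 sequences will be used for each hearing device". It explains recruitment beyond 14 as follows: "we will recruit up to 50 subjects which will give more power so that the interactions can be estimated more accurately".

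The condition list in Section IV.D has 15 conditions: five speech/noise configurations, each with a comparator (CI only, or no device in condition 10), the hearing aid and the CROS. Condition 11, for example, is "Speech presented at non-CI side (CI+HA ON) and noise presented at CI-ear (+90° and -90"°), and condition 8 is "Speech presented to the front, noise presented diffusely (CI+HA ON"). No text maps these conditions to the model factors or says that any are left out.

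**The concern.** Hypothesis 2 and Aim 2 ask how performance and device benefit change as the speech and noise positions change. The two device-by-location interactions are the terms that answer this. If the factor levels do not describe the conditions tested, someone must decide at analysis which conditions enter and under which label, and the plan gives no rule.

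Two consequences are specific:

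- Coding conditions 11 and 12 under the written noise label would report noise at the CI ear as noise at the CROS side, which is the opposite geometry.
- Depending on how the factors are repaired, the overall device effect can give no weight to conditions 2 and 3 (speech opposite the implant, diffuse noise). These belong to the study question stated in Sections I and IV.G.

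**Working it through.** **The plan's own figure.** Inputs from Section IV.F: difference 2 dB, SD 3.2 dB, alpha 0.05, 14 subjects, 90% power. Assumptions: two-sided test, 3.2 dB is the residual SD, errors independent given subject, and eight periods means k = 4 observations per device. For a contrast with cell weights w, SE = s × √(Σw²/n) and df = 2kn − n − (2k − 1); power is from the noncentral t. With equal weights, Σw² = 8 × (1/4)² = 0.5, SE = 3.2 × √(0.5/14) = 0.605, df = 91, and power is 90.5%. The stated 90% therefore corresponds to four configurations per device, whereas five are listed.

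**Mapping the ten HA/CROS conditions to the factors.**

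| Conditions (HA, CROS) | Speech | Noise | Fits as written | Fits if noise level is CI ear |
|---|---|---|---|---|
| 2, 3 | non-CI side | diffuse | yes | yes |
| 5, 6 | CI side | diffuse | yes | yes |
| 8, 9 | front | diffuse | no | no |
| 11, 12 | non-CI side | CI ear | no | yes |
| 14, 15 | front | front | no | no |

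**Estimability.** The fixed effects have six columns: intercept, device, signal, noise, device × signal, device × noise.

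- As written (2, 3, 5, 6): rank 4 of 6. Noise is constant, so noise and device × noise are lost; device, signal and device × signal remain.
- Noise level changed to CI ear (adds 11, 12): rank 6 of 6, with four conditions still unplaced.
- Front level added to both factors as well: all ten conditions enter, rank 10 of 10.
- One five-level configuration factor crossed with device: rank 10 of 10, and the same fit as the previous line.

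**Weights in the overall device effect.** Let d1 to d5 be the CROS-minus-HA differences for pairs 2-3, 5-6, 8-9, 11-12 and 14-15. With three-level factors (reference: CI-side speech, diffuse noise), the device terms are: base d2; signal opposite d1 − d2; signal front d3 − d2; noise at CI ear d4 − d1; noise in front d5 − d3. Averaging equally over factor levels:

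d2 + (d1 − d2 + d3 − d2)/3 + (d4 − d1 + d5 − d3)/3 = (d2 + d4 + d5)/3.

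Pairs 2-3 and 8-9 get zero weight. If only the ear is relabelled, d2 + (d1 − d2)/2 + (d4 − d1)/2 = (d2 + d4)/2, so pair 2-3 again gets zero.

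Over the ten cells, Σw² is 6 × (1/3)² = 0.667, against 10 × (1/5)² = 0.400 for equal configuration weights. The variance ratio is 0.667/0.400 = 1.67.

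**Power for 2 dB, k = 5.** The plan sets 2 dB for the device difference; applying it to the other contrasts is an assumption made here. An SD of 2.26 dB is 3.2/√2, the residual SD if half of the variance is between subjects.

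| Contrast | Σw² | SD 3.2: n=14 | SD 3.2: n=50 | SD 2.26: n=14 | SD 2.26: n=50 |
|---|---|---|---|---|---|
| Device, equal fifths | 0.400 | 95.6% | >99.9% | 99.9% | >99.9% |
| Device, level-averaged three-level factors | 0.667 | 81.1% | >99.9% | 98.0% | >99.9% |
| Device within one configuration | 2 | 37.5% | 87.7% | 64.0% | 99.3% |
| Device × noise, (12−11)−(3−2) | 4 | 21.3% | 59.7% | 37.5% | 87.7% |

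For example, device × noise at n = 14 and SD 3.2 has SE = 3.2 × √(4/14) = 1.710.

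**The case against.** The strongest reply is that non-CI ear is simply a slip. The only lateral noise listed is at the CI ear, and changing one word restores both noise terms. That is true, but it does not settle the matter. Four of the ten conditions still have no level, and the slip is not certain: the background in Section II singles out noise on the CROS side as the case where CROS helps little. That statement concerns unilateral hearing loss rather than implant users, so it is weak support for a deliberate choice, but it prevents a silent correction. Reading the ±90° note in conditions 10 to 12 as noise from both sides would not produce noise directed at the non-CI ear either.

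A third explanation is plausible. The 2 × 2 × 2 factors give eight cells, matching the eight periods, so the SAP may describe a different layout from the condition list. This is an inference, and it strengthens the case for reconciliation.

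Three limits stand. The device main effect, the only effect with a stated power, is estimable under every reading. The zero weights arise only if overall means averaging equally over factor levels, which the plan does not say; even then, pair 11-12, also with speech opposite the implant, keeps weight 1/3 or 1/2. The gap between 81.1% and 95.6% disappears at 50 subjects.

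**Conclusion.** The concern holds and should be resolved before analysis. As written, the primary model accommodates 4 of the 10 HA/CROS conditions and cannot estimate noise or device-by-noise. With the ear relabelled it accommodates 6 of 10, and conditions 8, 9, 14 and 15 remain unplaced. The loss of the noise terms depends on the literal wording; the missing front level does not. Device, signal and device-by-signal are estimable in both cases.

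These counts and ranks follow from the documents alone. The power figures rest on the residual SD and on the 2 dB target for each contrast. They indicate that device-by-noise is far less precisely estimated than the device effect: between 59.7% and 87.7% power at 50 subjects over the two SDs considered. The documents do not show which section is right.

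**What to change.** Reconcile Section IV.F with the condition list in Section IV.D and confirm the intended noise position. If the condition list stands:

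- Replace the two location factors with one five-level speech/noise configuration factor crossed with device.
- Pre-specify the CROS-minus-HA contrast within each configuration.
- Pre-specify the device-by-noise contrasts between configurations that share a speech position: (12 − 11) − (3 − 2) for CI-ear against diffuse noise, and (15 − 14) − (9 − 8) for front against diffuse noise.
- State the weights of the overall device effect, for example one fifth per configuration. Separate three-level factors fit the same means, but their level-averaged device effect has the zero weights shown, and reading their noise terms as general assumes no signal-by-noise interaction.
- Draw no conclusion about noise at the non-CI side unless it is tested.
- Say how the five comparator conditions (1, 4, 7, 10, 13), which have no level in the device factor, will be analysed.
- Align the eight-period description with the listed layout and rerun the power simulation for the chosen contrasts.

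The cost is SAP wording, model code and one simulation rerun.

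If the SAP's noise position is intended, the condition list must change, and the front conditions still need a place in the model. At the stated 10 minutes per condition, one added HA and CROS pair takes 20 minutes. The timed procedures in Section IV.D already sum to 15 + 10 + 20 + 30 + 150 = 225 minutes, so the total becomes 245 against the four hours (240 minutes) expected in Section IV.C. A comparator condition, or a second speech position, would add more.
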